7.3 Blinding and Allocation/Randomization

Subjects will be randomized into the study provided they have satisfied all subject selection criteria.

All subjects will be centrally randomized using an Interactive Response Technology (IRT).

The investigator's knowledge of the product allocation should not influence the decision to enroll a subject or affect the order in which subjects are enrolled.

This study is described as examiner-blind only (the examiner(s) will be blinded to the product received). Study subjects may be unblinded due to the presence of mouthwash in the Test Group. To ensure the examiner remains blinded throughout the study, staff involved in the preparation, dispensing of study products and in sharing the Exit Satisfaction Survey Questionnaire will work in a separate area.

Subjects will be instructed not to remove study products from the opaque bags provided/cartons outside of the dispensing room, while at the study site. Dispensing staff will not be involved in any efficacy/safety assessment procedures during the study.

Eligible subjects will be stratified according to their sex (male or female) to ensure a balance of sex across both treatment groups and then randomized to study product. This will give rise to two strata:

- Stratum 1: Sex = Male
- Stratum 2: Sex = Female

However, investigator site staff involved in safety or efficacy assessments, other employees of the Sponsor (including the clinical research scientist (CRS) and study statistician(s)) and vendors acting on behalf of the sponsor who may influence study outcomes will also be blinded to treatment allocation.

Site staff will be instructed to not enter any information into the clinical database that could potentially unblind study personnel.

7.4 Breaking the Blind

In case of an emergency, the investigator has the sole responsibility for determining if unblinding of a subject's product assignment is warranted. Subject safety must always be the first consideration in making such a determination. If the investigator decides that unblinding is warranted, the investigator should make every effort to contact the sponsor prior to unblinding a subject's product assignment unless this could delay emergency treatment of the subject.

Property of Haleon- Confidential

May not be used, divulged, published or otherwise disclosed without the consent of Haleon

CCI [REDACTED] Abbreviated Clinical Protocol Template v1.0

If a subject's product assignment is unblinded, the sponsor must be notified within 24 hours after breaking the blind. The date and reason that the blind was broken must be recorded in the source documentation and case report form, as applicable.

8 STATISTICAL CONSIDERATIONS AND DATA ANALYSES

8.1 Sample Size Determination

Sufficient subjects will be screened so that approximately 198 subjects are randomized (approximately 66 per group) to ensure approximately 180 (approximately 60 per group) evaluable subjects complete the entire study (allowing for 10% for drop-outs post-baseline).

The study will be sufficiently powered to demonstrate statistically significant differences between group Toothpaste/Mouthwash (a toothpaste containing 0.454% w/w SnF₂ with a mouthwash containing 0.07% w/w CPC) compared to the negative control (a toothpaste containing 0.243% w/w sodium fluoride) for mean NBS (overall) at Week 12 (primary objective). CCI

CCI

The dropout rate and SD estimates are based on the review of the sponsor clinical study evaluating 0.454% SnF₂ toothpastes (Haleon study 205045). As the estimate was based on only one study, the sample size was inflated from the initial calculation to account for this.

8.2 Populations for Analysis

8.2.1 Definitions of Analysis Populations

The Safety population will comprise all randomized subjects who receive at least one dose of investigational product. Summaries and analyses of this population will be based on the investigational product the subject received.

The primary population for the assessment of efficacy will be a modified intention-to-treat (mITT) population. The mITT population will comprise all randomized subjects who receive at least one dose of investigational product and complete at least one post-Baseline efficacy assessment. This population will be based on the investigational product the subject was randomized to. All subjects who receive a randomization number will be considered randomized.

The Per-Protocol (PP) population will comprise all subjects in the mITT population who have at least one non-missing efficacy assessment considered to be unaffected by protocol deviations.

The repeatability population for MGI is defined as all subjects who have at least one repeat MGI clinical assessment at any visit.

The repeatability population for TPI is defined as all subjects who have at least one repeat TPI clinical assessment at any visit.

8.2.2 Exclusions of Data from Analysis

Exclusion of any data from the analyses will be agreed during a Blinded Data Review (BDR) Meeting prior to database lock. Any reasons for exclusion of a subject from an analysis population or data from an analysis will be listed, if applicable.

A PP analysis will be performed for the primary endpoint if $\geq 10\%$ subjects in the mITT population are excluded from the PP population. Efficacy data determined to have been potentially impacted by a protocol deviation will be excluded from the PP analysis. The decisions as to whether or not a protocol deviation impacts efficacy data and whether to perform a PP analysis will be made during BDR, prior to database lock.

8.3 Statistical Analyses

Additional details of the proposed statistical analysis will be documented in the statistical analysis plan (SAP), which will be written following finalization of the protocol and prior to study unblinding/analysis (as appropriate). This section is a detailed summary of the planned statistical analyses of the primary and key secondary endpoints and a brief summary of how other collected data will be analyzed.

The mITT population will be used for all efficacy analyses.

All p-values presented will be two-sided and assessed at the 5% significance level. A sequential testing strategy will be used to adjust for the comparisons between the Toothpaste/Mouthwash combination and the Negative Control groups in overall NBS and interproximal NBS at each assessment time point.

At each time point, the interproximal NBS will only be assessed for confirmatory evidence if the overall NBS achieves a statistically significant greater reduction for the Toothpaste/Mouthwash combination group compared to the Negative Control group. This strategy will begin at Week 12, then move to Week 6, only moving to the earlier time point for confirmatory evidence if the Week 12 time point achieves statistically significant greater reductions for the group Toothpaste/Mouthwash compared to the Negative Control for both overall NBS and interproximal NBS. There will be no further adjustments for multiplicity for the other secondary endpoints.

Summary statistics (mean, median, SE, SD, minimum, maximum) will be presented for the primary and secondary endpoints at each assessment time point for both the observed value and change from baseline.

The observed margin (OM) option in SAS will be used when estimating least square means/performing MMRM analysis.

8.3.1 Primary Endpoint Analysis(es)

The primary endpoint of this study is NBS at Week 12; the primary hypothesis test will be the comparison between the Toothpaste/Mouthwash (a toothpaste containing 0.454% w/w SnF2

Property of Haleon- Confidential

May not be used, divulged, published or otherwise disclosed without the consent of Haleon

CCI

Abbreviated Clinical Protocol Template v1.0

with a mouthwash containing 0.07% w/w CPC) group and the negative control (a toothpaste containing 0.243% w/w NaF) group in the mITT population.

The NBS (overall) for each subject at each visit is calculated as the number of evaluable tooth sites with a BI score of either 1 or 2.

NBS (overall) at Week 12 will be analysed using a Mixed Model with Repeated Measures (MMRM) with investigational product, visit and [investigational product x visit] interaction as fixed effects, and Baseline NBS as a covariate. Subject will be included as a repeated measure with unstructured covariance matrix. Kenward Rogers degrees of freedom approach will be applied (Kenward, 1997). The least squares differences at Week 12 from the MMRM will be presented, along with the two-sided p-value and 95% CIs.

The assumptions of normality and homogeneity of variance in the MMRM will be investigated. In case of violation of these assumptions, a suitable non-parametric test (adjusted for the randomization stratification) will be performed and the results will be provided to support the MMRM results.

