### 4.4.1.2 Statistical Hypothesis, Model and Method of Analysis

The primary hypothesis test will be the comparison between the Toothpaste/Mouthwash and the Negative Control in the mITT population.

The following null and alternative hypotheses will be evaluated:

- H0: There is no difference in the Overall NBS at 12 weeks between the Toothpaste/Mouthwash and Negative Control.

Haleon Confidential

CCI Statistical Analysis Plan Template v7.0

Page 20 of 44

- H1: There is a difference in the Overall NBS at 12 weeks between the Toothpaste/Mouthwash and Negative Control.

A Mixed Model for Repeated Measures (MMRM) will be used, with Overall NBS values as the dependent/response variable, the categorical time point Week 12, treatment group (Toothpaste/Mouthwash and Negative Control) and treatment group by time point interaction as fixed effects and baseline Overall NBS as a covariate. Gender will also be included as stratification factor. Subject will be included as a repeated measure with an unstructured covariance matrix. The Kenward Roger degrees of freedom approach will be applied. If unstructured covariance matrix does not converge, the following covariance structures will be applied in order until convergence is achieved: 1) Toeplitz, 2) compound symmetry (CS).

Using the above model, the least squares differences at Week 12 from the MMRM will be presented, along with the two-sided p-value and 95% CI in Table 14.2.2.2.1. The % adjusted mean difference will also be presented.

The assumption of normality and homogeneity of variance in the MMRM will be investigated. In case of violation of these assumptions, a suitable non-parametric test (van Elteren test adjusting for gender stratification) will be performed for between product comparison to support the MMRM results.

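### The MMRM holds the baseline slope equal at Weeks 6 and 12; a baseline x visit term costs almost nothing and protects Week 12 precision if the slopes differ

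*Protocol*

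**What the plan says.** Protocol 8.3.1 analyses overall NBS at Week 12 with an MMRM. The terms are investigational product, visit and the product-by-visit "interaction as fixed effects, and Baseline NBS as a covariate". On covariance it says "Subject will be included as a repeated measure with unstructured covariance matrix".

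SAP 4.4.1.2 has the same structure, with "treatment group by time point interaction as fixed effects and baseline Overall NBS as a covariate". It adds sex ("Gender will also be included as stratification factor"). It describes the time factor as "the categorical time point Week 12", without naming Week 6.

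Neither document has a baseline x visit term, and SAP Table 5-1 (changes from the protocol) does not touch the point. Protocol 8.3.2 and 8.3.4 and SAP 4.4.2 and 4.4.3 reuse the model for interproximal NBS, EBI, MGI and TPI and for all three product comparisons, replacing only the baseline covariate.

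**The concern.** The model is flexible by visit everywhere except in the baseline adjustment. Product-by-visit frees the treatment effect and the unstructured matrix frees the variances and covariance, but a single coefficient carries baseline NBS into both Week 6 and Week 12.

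If the two true slopes differ, the fitted slope is a compromise. The unstructured covariance sets the weights, so the compromise can lie close to the Week 6 slope. Week 12, the primary visit, is then adjusted with a slope that is not its own. Part of the outcome variation that baseline could explain stays in the residual, and the Week 12 interval may be somewhat wider than it need be. Only precision is at stake.

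**Working it through.** **1. Are both visits in the model?** Yes, on a fair reading. Protocol 8.3.1 has visit and product-by-visit as effects and a repeated measure on subject. Protocol 8.3.2 takes the Week 6 results from the same model. SAP 4.4.2.1.1 reports Week 6 overall NBS in Table 14.2.2.2.1, the table that also holds the primary result. A time-point interaction and an unstructured matrix have no meaning with one time point. The common slope is therefore a real feature of the planned model.

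**2. The plan's own figures.** The randomized number is 60 x 1.10 = 66 per group, 198 in all; dividing by the completion rate gives 180/0.90 = 200, so the stated figure is reproduced approximately. The power calculation is redacted. No slope or correlation is given, and no SD is visible. Everything below uses assumed values.

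**3. Formula.** Let b6 and b12 be the true baseline slopes, and S the residual covariance of Weeks 6 and 12 given baseline, with entries S11, S12, S22. In large samples the common slope tends to

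bc = [(S22 − S12)·b6 + (S11 − S12)·b12] / (S11 + S22 − 2·S12).

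The Week 12 variance, planned model relative to a model with visit-specific slopes, is

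ratio = 1 + Var(B)·(b12 − bc)² / S22.

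The leftover term in the treatment contrast is (b12 − bc) times the difference in baseline means between arms. Randomization gives that difference expectation zero, so the term adds variance and not bias.

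**4. Results in NBS units.** Assumed: baseline uniform on 17–50 (10–30% of 168 sites), so Var(B) = 33²/12 = 90.75; residual SDs and correlation r as shown.

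| Slopes W6 / W12 | SD W6 / W12 | r | bc | Ratio |
|---|---|---|---|---|
| equal | any | any | same | 1.000 |
| 0.6 / 0.5 | 8 / 8 | 0.7 | 0.550 | 1.004 |
| 0.6 / 0.4 | 8 / 8 | 0.7 | 0.500 | 1.014 |
| 0.7 / 0.4 | 8 / 8 | 0.8 | 0.550 | 1.032 |
| 0.6 / 0.4 | 7 / 9 | 0.8 | 0.610 | 1.049 |
| 0.7 / 0.4 | 7 / 9 | 0.8 | 0.714 | 1.111 |
| 0.6 / 0.4 | 9 / 7 | 0.8 | 0.390 | 1.0002 |
| 0.7 / 0.4 | 9 / 7 | 0.8 | 0.386 | 1.0004 |

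Worked example, fifth row: S11 = 49, S22 = 81, S12 = 0.8 x 7 x 9 = 50.4. Then bc = (30.6 x 0.6 − 1.4 x 0.4)/29.2 = 0.610, and the ratio is 1 + 90.75 x (0.4 − 0.610)²/81 = 1.049.

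The 7/9 and 9/7 rows lie near opposite ends. One weight is close to zero in each (49 − 50.4 = −1.4), so the common slope falls almost on the Week 6 slope or almost on the Week 12 slope.

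**5. Results in standardized units.** Assumed: baseline and both visits have SD 1, with correlations (baseline–Week 6, baseline–Week 12, Week 6–Week 12).

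| Correlations | Ratio | 80% power becomes |
|---|---|---|
| 0.5, 0.5, 0.7 | 1.000 | 80.0% |
| 0.5, 0.4, 0.7 | 1.004 | 79.9% |
| 0.4, 0.6, 0.7 | 1.007 | 79.8% |
| 0.5, 0.3, 0.7 | 1.018 | 79.3% |
| 0.6, 0.4, 0.7 | 1.022 | 79.1% |
| 0.6, 0.3, 0.7 | 1.058 | 77.8% |
| 0.7, 0.3, 0.6 | 1.116 | 75.6% |

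Power is Φ(2.80/√ratio − 1.96) at two-sided 5%. The 80% start is illustrative, because the planned power is redacted.

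**6. Simulation.** 3 arms x 66, 9% missing at Week 12 unrelated to outcome, 2,000 runs per setting. Both models estimated the Week 12 difference to within 0.01 SD of the truth. Type I error was 4.4–5.0% without the extra term and 4.4–4.8% in the unequal-slope settings with it (4.95% for both models when the slopes were equal). With equal slopes the mean standard error went from 0.1553 to 0.1555 when the term was added: 0.0002/0.1553 = 0.13%.

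**The case against.** The strongest reply is that no loss has been shown. It exists only if the slopes differ, and the documents have no slope, correlation or visible SD to say so. A single baseline covariate is a valid, pre-specified choice. This stands, and it limits the point to a refinement.

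The larger figures also depend on direction. Swapping the assumed SDs from 7/9 to 9/7 takes 4.9% to 0.02% and 11.1% to 0.04%, and nothing in the documents says which visit is the more variable. The baseline spread matters too. With an assumed baseline SD of 6, Var(B) is 36 and the losses scale by 36/90.75, so 4.9% becomes 2.0% and 11.1% becomes 4.4%. This also stands.

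A reader might infer that the prophylaxis makes the slopes differ. The schedule does not support that: it is given at Baseline before randomization, both modelled visits follow it, and no cleaning is planned between them. It may weaken the baseline relation at both visits without separating the slopes.

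A reader might also infer bias from adjusting with the wrong slope. Randomization and the simulation speak against it. The missing-at-random argument in protocol 8.3.7 and SAP 4.4.4 does presuppose an adequate mean model. The simulation did not test outcome-dependent dropout, but nothing in the documents shows a bias from this source.

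Finally, if only Week 12 were modelled, as the SAP's wording could suggest, there would be no common slope. That reading does not survive the repeated measure, the interaction and the Week 6 results in the same table.

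**Conclusion.** The point holds as a nearly free improvement. The planned model forces one baseline slope at two visits, and the Week 12 contrast may lose some precision if the true slopes differ. That the slopes do differ, or that precision is certainly lost, goes beyond the documents.

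Under assumed values the variance loss is:
- 0% with equal slopes;
- about 0–2% for gaps up to 0.2 with similar SDs, which is less than one power point;
- about 5–11% only for large gaps, or when Week 12 is the more variable visit and the between-visit correlation is high (11.6% in the most extreme case tried);
- near 0% in the cases tried with Week 6 as the more variable visit.

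A gap of 0.3 with equal residual SDs gave 3.2%, so a large gap alone does not always reach the upper range. The validity of the primary test and its type I error are not in question.

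**What to change.** In protocol 8.3.1 and SAP 4.4.1.2, state that both Week 6 and Week 12 enter the model, and add baseline NBS x visit to the fixed effects. Add the respective baseline x visit term to the models for interproximal NBS, EBI, MGI and TPI. Record the change in SAP Table 5-1 if only the SAP is amended.

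The cost is one degree of freedom per model and one term in the program. If the slopes turn out equal, the standard error grows by about 0.1%. No data collection or sample size changes.

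Make the change before unblinding so that it remains pre-specified. If unblinding has already taken place, keep the planned model as primary and report the extended one as a labelled sensitivity analysis.

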8.3.2 Secondary Endpoint Analysis(es)

The secondary endpoints comparing the Toothpaste/Mouthwash (a toothpaste containing 0.454% w/w SnF₂ with a mouthwash containing 0.07% w/w CPC) and the negative control (a toothpaste containing 0.243% w/w sodium fluoride) will be analyzed using the same MMRM model described above for the primary endpoint (mITT population), but with Baseline overall NBS replaced with the Baseline of the respective endpoint as follows:

Baseline interproximal NBS for interproximal NBS at Week 12

Baseline interproximal NBS for interproximal NBS at Week 6

Baseline Mean overall BI for Mean overall BI at Week 12

Baseline Mean interproximal BI for Mean interproximal BI at Week 12

Baseline Mean overall BI for Mean overall BI at Week 6

Baseline Mean interproximal BI for Mean interproximal BI at Week 6

Baseline Mean overall MGI for Mean overall MGI at Week 12

Baseline Mean interproximal MGI for Mean interproximal MGI at Week 12

Baseline Mean overall MGI for Mean overall MGI at Week 6

Baseline Mean interproximal MGI for Mean interproximal MGI at Week 6

Baseline Mean overall TPI for Mean overall TPI at Week 12

Baseline Mean interproximal TPI for Mean interproximal TPI at Week 12

Baseline Mean overall TPI for Mean overall TPI at Week 6

Baseline Mean interproximal TPI for Mean interproximal TPI at Week 6

For the secondary endpoint of overall NBS at Week 6, Baseline overall NBS will remain in the model.

Property of Haleon- Confidential

May not be used, divulged, published or otherwise disclosed without the consent of Haleon

CCI

Abbreviated Clinical Protocol Template v1.0

The secondary endpoints comparing the SnF₂ Toothpaste alone (a toothpaste containing 0.454% w/w SnF₂) to the negative control (a toothpaste containing 0.243% w/w sodium fluoride) will be analysed using the same MMRM model described above.

8.3.3 Safety Analysis(es)

Safety analyses will be performed on the Safety population, according to investigational product received. AEs will be regarded as ‘treatment emergent’ if they occur on or after the first use of investigational product at Baseline. In the event of a missing start date, an AE will be assumed to be ‘treatment emergent’ unless the end date is prior to starting treatment. In case of misallocation, compared to the randomization schedule, TEAEs will be associated with the most recent study investigational received.

Each AE will be categorized as oral or non-oral by the investigator or medically qualified designee. All will be reviewed by the CRS and coded using the MedDRA prior to database lock and unblinding.

A listing of all AEs will be presented for all subjects in the Safety population with the following AE summaries (number of distinct AEs and frequency/proportion of subjects affected) presented by treatment group and overall:

- TEAEs
- TEAEs by System Organ Class (SOC) and Preferred Term (PT)
- TEAEs by Oral/Non-Oral and PT
- Treatment emergent treatment related AEs by Oral/Non-Oral and PT
- Treatment emergent treatment related serious AEs by SOC and PT

Separate listings will be presented for:

- Deaths, SAEs and any AEs leading to product or study discontinuation.
- OST findings (with a summary of abnormalities by visit)

8.3.4 Other Analysis(es)

Exploratory Analysis(es)

Toothpaste/Mouthwash Compared to Reference Toothpaste

The exploratory endpoints comparing the Toothpaste/Mouthwash (a toothpaste containing 0.454% w/w SnF₂ with a mouthwash containing 0.07% w/w CPC) to the SnF₂ Toothpaste (toothpaste containing 0.454% w/w SnF₂) will be analysed using the same MMRM model described above for the primary and secondary endpoints.

Exit Satisfaction Survey Questionnaire (toothpaste/mouthwash treatment arm)

A summary of the number and percentage of subjects reporting at each level of the NRS and the cumulative number of subjects reporting at each level or higher at Week 12 will be presented, and the numeric (integer) NRS score at Week 12 will be summarized descriptively, by the test product toothpaste and the test product mouthwash.

Property of Haleon- Confidential

May not be used, divulged, published or otherwise disclosed without the consent of Haleon

CCI

Abbreviated Clinical Protocol Template v1.0

Subject free text comments will be listed after each NRS rating.

In addition to each NRS, subjects will be asked whether they would recommend the products to their family and friends who have gum problems at the end of the study. Responses (“yes” or “no”) will be summarised by the number and percentage of subjects in the test product toothpaste and the test product mouthwash treatment respectively.

Repeatability of Examiner

The repeatability of the examiner in conducting the MGI and TPI assessments will also be performed for a random sample of subjects. The repeat assessments will be compared to the original assessments. The repeat assessments will not to be used in any efficacy analysis.

The first and second assessments of each index will be analyzed with a Fleiss-Cohen weighted kappa coefficient (κ), along with the 95% CI, to assess the intra-examiner reliability. Reliability will be deemed: Excellent if $\kappa > 0.75$, Fair to good if $0.4 \leq \kappa \leq 0.75$ and Poor if $\kappa < 0.4$. This analysis will be conducted on each respective index repeatability population (MGI population and TPI population).

